13.4. Algorithm for classification of Prohibited medications

Table 5: Algorithm for Prohibited medications.

1 st condition: ATC2 code	2 nd condition: Route of administration	3 rd condition: Taken during the study (i.e. that ends on or after the IC signature date)		
		MEDICATION start date	MEDICATION end date	RULE for classification in Prohibited Medications / Concomitant d
ATC2=S01 ("OPHTHALMOLOGICALS")	"Topical" OR "Intraocular" OR "Nasal" OR "Other"	Known	Known	If stop date ≤ IC date, then PROHIBITED=No If stop date > IC date, then PROHIBITED=Yes
			Partial	Impute stop date as latest possible date (i.e. last day of month if only day is missing, Dec if only month is missing, 31 st Dec if day and month are both missing, then: If stop date ≤ IC date, then PROHIBITED=No If stop date > IC date, then PROHIBITED=Yes
			Missing	PROHIBITED=Yes
		Partial OR Missing	Known	If stop date ≤ IC date, then PROHIBITED=No If stop date > IC date, then PROHIBITED=Yes
			Partial	Impute stop date as latest possible date (i.e. last day of month if only day is missing, Dec if only month is missing, 31 st Dec if day and month are both missing, then: If stop date ≤ IC date, then PROHIBITED=No If stop date > IC date, then PROHIBITED=Yes
			Missing	PROHIBITED=Yes

Note 1: All three conditions need to be satisfied to classify the medication as PROHIBITED

Note 2: To identify the impacted measurements taken within one week after taking these prohibited medications, if the medication start date is partial, the earliest possible date (i.e. first day of month if only day is missing, Jan if only month is missing, 1st Jan if day and month are both missing) will be imputed.

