3.2 PRIMARY AND KEY SECONDARY ESTIMANDS

3.2.1 Primary Estimand

The estimand for the primary objective is defined as follows:

- Treatment: 4 weeks follow up after 4 weeks of TID administration of rhNGF new formulation (two concentrations and vehicle).
- Population: Male and female patients aged ≥ 18 years with dry eye. Full Analysis Set.
- Variable: mean change from baseline to week 8 in symptoms of dry eye assessed by SANDE Global Score.
- Intercurrent events (ICEs) and strategies to handle them:
 - Treatment discontinuation: a treatment policy strategy will be applied where all the observed values will be used regardless of the occurrence of the ICEs. Missing data due to any reason will be handled by using a multiple imputation with a copy-reference approach (see § 10.6.2 for further details).
 - Use of a prohibited medication, as listed in § 6.6.1, in the week before any assessment of SANDE Global Score: a hypothetical strategy will be applied where any data collected in the week after the occurrence of the ICE will be discarded. Missing data will be imputed by using a multiple imputation with copy-reference approach (see § 10.6.2 for further details).
- Population-level summary: difference in mean change from baseline to week 8 in symptoms of dry eye assessed by SANDE Global Score between each concentration group of IMP (groups IMP1 and IMP2) and the vehicle group as derived by the Mixed Model for repeated measures defined in § 10.6.2.

In summary, the primary estimand is defined as the difference in mean change from baseline to week 8 in symptoms of dry eye assessed by SANDE Global Score between treatments in the targeted patient population regardless of study treatment discontinuation and had prohibited medications not been available to subjects in the week before any study evaluation.

More details are provided in the statistical § 10.

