7.1.3. Prohibited Medications

During the whole period of the participation to the trial (about 10 weeks) patients should not use ophthalmic steroids, ophthalmic immunomodulators such as cyclosporine A and lifitegrast, intranasal tear-secretagogues such as varenicline, ophthalmic topical anti-histamine, any derivatives of nerve growth factor, or any medications as part of another clinical trial. The use of

artificial tears - lubricating CCI not provided by the Sponsor is also forbidden. Patients should not use punctal plugs, contact lenses (including scleral lenses), moisture goggles, warm compresses or electro/magnetic stimulation devices on the eye, face or scalp.

The algorithm for the identification of the prohibited medications taken during the study has been reported in [Appendix 13.4](#).

Before the study unmasking, a masked review of the concomitant medications taken by the patients during the study will be done in order to verify the presence of prohibited medications; their frequency and dosage will also be considered in order to define the severity of the deviation.

Prohibited medications will be summarized based on FAS according to the planned treatment. Ophthalmic prohibited medications will be summarized separately from non-ophthalmic prohibited medications. Ophthalmic prohibited medications will be summarized for the study eye and fellow eye separately.

A by-patient listing of prohibited medications will be presented by treatment.

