7.2. Prior and Concomitant Procedures

Prior and concomitant procedures will be coded using the latest version of MedDRA during the study. Ophthalmic and non-ophthalmic procedures will be summarized based on the FAS according to the planned treatment, sorted by system organ class (SOC) and PT, with SOC's sorted alphabetically and PTs within each SOC in descending order of frequency.

By-patient listings of prior and concomitant ophthalmic and non-ophthalmic procedures will be presented by site.

Partial missing start or end dates will be imputed as described in [Appendix 13.2](#) for medications analysis.

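### SAP Table 5 recognises only S01-coded drugs, so the non-drug therapies on the protocol's prohibited list have no route to intercurrent-event handling

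*SAP*

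**What the plan says.** Protocol 3.2.1 names the second intercurrent event of the primary estimand as "Use of a prohibited medication, as listed in § 6.6.1, in the week before any assessment of SANDE Global Score" and handles it with a hypothetical strategy: values from the week after the event are dropped and imputed. Protocol 3.2.2 does the same for the three key secondary endpoints at Week 4.

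Protocol 6.6.1 lists drugs and also non-drug measures. SAP 7.1.3 repeats the list under its Prohibited Medications heading, including that patients "should not use punctal plugs, contact lenses (including scleral lenses), moisture goggles, warm compresses or electro/magnetic stimulation devices on the eye, face or scalp". Medications taken as part of another trial and NGF derivatives are on the list too.

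SAP 7.1.3 then hands over detection: "The algorithm for the identification of the prohibited medications taken during the study has been reported in" Appendix 13.4. Table 5 in that appendix sets three conditions: ATC2 code S01; a route recorded as Topical, Intraocular, Nasal or Other; and a stop date after consent (or a missing one). Its first note reads: "Note 1: All three conditions need to be satisfied to classify the medication as PROHIBITED".

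Two other SAP sections bear on the point. SAP 7.2 says: "Prior and concomitant procedures will be coded using the latest version of MedDRA during the study". SAP 7.1.3 adds that a "masked review of the concomitant medications taken by the patients during the study will be done" before unmasking, to verify prohibited medications and grade the deviation.

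**The concern.** The definition and the tool that implements it do not match. The protocol's event is the whole 6.6.1 list; the SAP's detector sees only one drug class with four route values. A patient fitted with punctal plugs during follow-up keeps the Week 8 SANDE score as ordinary data. A patient who used a detected non-sponsor artificial tear in the week before Week 8 has that score set to missing and imputed from the vehicle group.

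The missed items are not inert. Protocol 2.6.1 says that punctal plugs reduce tear drainage, maintaining the tear lake to increase wetting of the ocular surface. That plausibly affects symptoms, Schirmer-I and staining. Such measures are also what a symptomatic patient might turn to when other drops are forbidden. If they count as prohibited therapy, the primary analysis does not fully apply the hypothetical strategy it states.

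**Working it through.** **1. Tracing the list through the rules.**

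| Item in Protocol 6.6.1 | Can Table 5 flag it? | Handled as intercurrent event? | Route out of Per Protocol set |
|---|---|---|---|
| S01-coded product with a listed route | Yes, if the date condition is met | Yes, within the one-week rule | Automatic major deviation (SAP 5.2) |
| Plugs, lenses, goggles, compresses, stimulation devices | No: not coded drugs; if entered as procedures, coded in MedDRA (SAP 7.2) | No | CTMS deviation plus masked review only |
| Other-trial medication without an S01 code or a listed route (for example, taken orally) | No | No | CTMS deviation plus masked review only |

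No SAP rule links procedure or deviation records to the Table 5 flag. The same flag feeds the primary analysis (8.1.1), the sensitivity analyses that first apply the hypothetical strategy (8.1.2), both modified strategies (8.1.3) and the Week 4 key secondary endpoints (8.2.1). SANDE Global Score at Week 4 also follows the primary strategy (8.2.2.1).

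**2. Was the narrowing declared?** SAP 3.3.1 drops the protocol's cross-reference to 6.6.1, and SAP section 1 makes the SAP govern where the two differ. The visible text of SAP section 11 declares one change, which concerns the status of a Week 8 endpoint. It does not mention the intercurrent event.

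**3. Signs inside the SAP that the filter is narrower than intended.** SAP 7.1.3 plans a separate summary of non-ophthalmic prohibited medications, which fits poorly with a filter restricted to ophthalmologicals. Table 5 has no Ocular or Ophthalmic route value, yet the SAP's own product tables (3.4.1 and 3.4.2) describe routes as ocular and topical ocular. Whether this loses any eye drops depends on eCRF values that the documents do not show.

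**4. Size.** The documents give no rate of use, so this is illustration only.

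The plan's own figure comes first. Inputs from Protocol 10.1 are mean changes -28.2 and -17.4 (difference 10.8), SDs 26.36 and 20.29, one-sided alpha 0.0125 and power 80%.
- Common SD = √((26.36² + 20.29²)/2) = 23.52.
- n per group = 2 × SD² × (z₀.₉₈₇₅ + z₀.₈₀)² / 10.8² gives 91 by the normal formula; a Welch t calculation gives 92. The plan states 92, so it reproduces.
- Power per comparison at 92 per group is 80.9% (normal) or 80.2% (Welch).

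Now assume that a fraction f of vehicle patients gains g points from an undetected measure and no active patient does. The expected difference is 10.8 − f × g.
- f = 1%, g = 5: 10.8 − 0.05 = 10.75; power 80.5%.
- f = 5%, g = 10.8: 10.8 − 0.54 = 10.26; power 76.3%.
- f = 10%, g = 10.8: 10.8 − 1.08 = 9.72; power 71.3%.

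Powers use the normal formula. With equal use and equal benefit in all arms the shift is zero. Use confined to one active arm would widen that arm's difference by the same amount.

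**The case against.** The strongest counter-argument is the word medication. Both documents name the event as use of a prohibited medication, and related text speaks of intake and administration. Protocol 6.6.1 puts the devices in their own sentence and then describes a review of concomitant medication only. One could coherently leave device use under observed-data handling. This stands as an ambiguity. It does not settle the matter, because the protocol defines the term by the 6.6.1 list and the SAP places the devices under its Prohibited Medications heading. Either reading needs an edit.

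A reader might also infer three stronger things that the documents do not support.

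- *That these patients can never be excluded from the Per Protocol set.* SAP 5.2 takes deviations from CTMS as well as SAS programming, reviews all of them masked, classes them by potential bias and excludes patients with major ones. SAP 4.3.5 leaves the reasons to the masked Data Review Meeting. Such exclusion is possible but not automatic; it depends on site reporting and judgement. It also decides Per Protocol membership only and sets no value in the Full Analysis Set to missing. Exclusion criterion 16 covers lenses and plugs, but the schedule checks eligibility at Visits 1 and 2 only.
- *That the gap changes the Week 8 Schirmer-I and staining analyses.* SAP 8.2.2 analyses secondary endpoints on observed data whatever intercurrent events occur, so a wider algorithm would not alter them. The key secondary Schirmer-I and staining endpoints are at Week 4, before follow-up starts.
- *That specific listed drugs are certainly missed.* Whether NGF derivatives or other listed drugs fall outside S01 needs a drug dictionary that is not in the documents. The masked medication review is a partial backstop for drugs, though its wording does not extend to devices.

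**Conclusion.** The point holds in this form: as written, Table 5 gives five listed non-drug therapies, and other-trial medications lacking an S01 code or a listed route, no path to the intercurrent-event handling of the primary endpoint or the Week 4 key secondary endpoints. Protocol 3.2.1 and 3.2.2 define the event by a list that contains them. This is a stated rule that contradicts the definition it implements, rather than detail left for later. In the Per Protocol set the defect is an asymmetry: drug intake flagged by Table 5 is automatically major, while device use relies on reporting and masked judgement.

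The size cannot be computed from the documents. It is zero under even use and benefit. Under the assumed vehicle-only scenarios above, the difference falls by 0.05 to 1.08 points, which works against rhNGF and so does not raise the risk of a false positive claim. The conclusion rests on reading the protocol's cross-reference to 6.6.1 as covering the whole list; if devices were never meant, what remains is an undeclared ambiguity. The point deserves correction before database lock, but nothing here shows that the trial's result would change.

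**What to change.** Before database lock and under masking, add a second branch to SAP 13.4:

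- Search procedure, device and deviation records, and classify as prohibited any entry that matches the 6.6.1 list.
- Classify any other-trial medication or NGF derivative as prohibited regardless of ATC code or route.
- Count the entry as an intercurrent event when the period of use, including ongoing use, overlaps the week before the assessment. Note 2 of SAP 13.4 addresses only the start date; a rule tied to the start would miss a plug placed in Week 5 and still in place at Week 8.
- Apply the same major-deviation flag as for drugs.
- Check that the four route values in Table 5 match how the eCRF records eye drops.

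If the sponsor does not intend devices to be intercurrent events, say so in SAP 3.3 and 7.1.3 and declare it in section 11 as a change from the protocol.

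The cost is SAP wording and a short masked term list. The downside is that a few more values may be set to missing and imputed.

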 - Use of a prohibited medication listed in § 6.6.1 in the week before any assessment of corneal fluorescein staining: a hypothetical strategy will be applied where any data collected in the week after the occurrence of the ICE will be discarded. Missing data will be imputed by using a multiple imputation with copy-reference approach (see § 10.6.3 for further details).
- Population-level summary: difference in mean change from baseline to week 4 in total corneal fluorescein staining (NEI scale) in the Study Eye as assessed by the investigator between each concentration group of IMP (groups IMP1 and IMP2) and the vehicle group as derived by an ANCOVA model defined in § 10.6.3.

In summary, the estimand for the key secondary objective #3 is defined as the difference in mean change from baseline to week 4 in total corneal fluorescein staining (NEI scale) in the Study Eye as assessed by the investigator between treatments in the targeted patient population regardless of study treatment discontinuation and had prohibited medications not been available to subjects in the week before any study evaluation.

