3.3.2. Key Secondary Estimands

Key secondary objective #1

The estimand for the key secondary objective #1 is defined as follows:

- Treatment: 4 weeks of CCI administration of rhNGF new formulation (CCI and vehicle).
- Population: Male and female patients aged ≥ 18 years with dry eye. Full Analysis Set.
- Variable: proportion of patients improving to Schirmer-I test without anesthesia ≥ 10 mm/5min in the Study Eye at week 4 (V4).
- ICEs and strategies to handle them:
 - Treatment discontinuation (only IMP): a treatment policy strategy will be applied where all the observed values will be used regardless of the occurrence of the ICEs. Missing data due to any reason will be handled by using a multiple imputation with a copy-reference approach (see [Section 8.2.1](#) for further details).
 - Use of a prohibited medication, in the week before any assessment of Schirmer-I score: a hypothetical strategy will be applied where any data collected in the week after the occurrence of the ICE will be discarded. Missing data for Schirmer-I score will be imputed by using a multiple imputation with copy-reference approach (see [Section 8.2.1](#) for further details), then the proportion of patients with an improvement ≥ 10 mm/5min in the Study Eye will be derived.
- Population-level summary: difference in proportion of patients improving to Schirmer-I test without anesthesia ≥ 10 mm/5min in the Study Eye at week 4 (V4) between each concentration group of IMP (groups IMP1 and IMP2) and the vehicle group as derived by a logistic model defined in [Section 8.2.1](#).

In summary, the estimand for the key secondary objective #1 is defined as the difference in proportion of patients improving to Schirmer-I test without anesthesia ≥ 10 mm/5min in the Study Eye at week 4 (V4) between treatments in the targeted patient population regardless of study treatment discontinuation and had prohibited medications not been available to patients in the week before any study evaluation.

Key secondary objective #2

The estimand for the key secondary objective #2 is defined as follows:

- Treatment: 4 weeks of CCI administration of rhNGF new formulation (CCI

- CCI and vehicle).
- Population: Male and female patients aged ≥ 18 years with dry eye. Full Analysis Set.
- Variable: mean change from baseline in Schirmer-I score without anesthesia in the Study Eye at week 4 (V4).
- ICEs and strategies to handle them:

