 - Treatment discontinuation (only IMP): a treatment policy strategy will be applied where all the observed values will be used regardless of the occurrence of the ICEs. Missing data due to any reason will be handled by using a multiple imputation with a copy-reference approach (see [Section 8.2.1](#) for further details).
 - Use of a prohibited medication, in the week before any assessment of Schirmer-I score: a hypothetical strategy will be applied where any data collected in the week after the occurrence of the ICE will be discarded. Missing data will be imputed by using a multiple imputation with copy-reference approach (see [Section 8.2.1](#) for further details).
- Population-level summary: difference in mean change from baseline to week 4 in Schirmer-I score without anesthesia in the Study Eye between each concentration group of IMP (groups IMP1 and IMP2) and the vehicle group as derived by an ANCOVA model defined in [Section 8.2.1](#).

In summary, the estimand for the key secondary objective #2 is defined as the difference in mean change from baseline to week 4 in Schirmer-I score without anesthesia in the Study Eye between treatments in the targeted patient population regardless of study treatment discontinuation and had prohibited medications not been available to patients in the week before any study evaluation.

Key secondary objective #3

The estimand for the key secondary objective #3 is defined as follows:

- Treatment: 4 weeks of CCI administration of rhNGF new formulation (CCI and vehicle).
- Population: Male and female patients aged ≥ 18 years with dry eye. Full Analysis Set.
- Variable: mean change from baseline in total CCI in the Study Eye as assessed by the investigator at week 4 (V4).
- ICEs and strategies to handle them:
 - Treatment discontinuation (only IMP): a treatment policy strategy will be applied where all the observed values will be used regardless of the occurrence of the ICEs. Missing data due to any reason will be handled by using a multiple imputation with a copy-reference approach (see [Section 8.2.1](#) for further details).
 - Use of a prohibited medication, in the week before any assessment of CCI a hypothetical strategy will be applied where any data collected in the week after the occurrence of the ICE will be discarded. Missing data will be imputed by using a multiple imputation with copy-reference approach (see [Section 8.2.1](#) for further details).

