Based on this modeling, LS Mean, SE, and two-sided 95% CI at Week 4 and Week 8 will be provided for each treatment arm (rhNGF \square mcg/mL, rhNGF \square mcg/mL, and vehicle); difference in LS means, two-sided 95% CI, and corresponding one-sided p-value will be provided for each comparison at each timepoint. P-values for the comparisons at Week 8 will be used to declare the superiority of at least one of the \square over vehicle.

LS means change from baseline and corresponding 95% CI at Week 8 will be plotted in a forest plot by treatment arm for all main and sensitivity analysis.

Descriptive statistics for SANDE Global Score at each visit will be presented based on observed data and data after applying hypothetical strategy.

Primary Estimand:

Missing data that may be obtained notwithstanding the intent to apply the treatment policy strategy and after having applied the hypothetical strategy when needed (see [Section 3.3.1](#)), will be addressed by using multiple imputation (MI) based on copy-reference approach. This approach does not assume benefits for the rhNGF in case of discontinuation and limits a post-discontinuation clinical effect to that of the vehicle. Specifically, the copy-reference approach will be implemented in this way:

- Intermittent and monotone missing data for SANDE Global Score at baseline, Week 4 and Week 8 will be imputed by using the Fully Conditional Specification (FCS) method under the missing not at random (MNAR) assumption where only the subset of observations that come from the Vehicle group are used to derive the imputation model. The missing pattern is assumed to be arbitrary. The PROC MI procedure and FCS REGRESSION statement will be used with the seed of 47292748 and 50 imputed datasets. The minimum and maximum imputed values will be restrained to 0 and 100, respectively, via MIN and MAX options. In case of convergence issues, after imputation, imputed values lower than 0 or greater than 100 will be set to 0 and 100, respectively. The imputed values will be rounded to integers.
- For each imputed dataset, the change from baseline at Week 4 and Week 8 is derived.

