Missing data will be imputed by using a multiple imputation with copy-reference approach (see [Section 8.1.1](#)). For each imputed dataset, the change from baseline at Week 4 is derived. Patients with change from baseline at Week 4 ≥ 10 mm/5min will be considered as having improvement while patients with change from baseline at Week 4 < 10 mm/5mins will be considered as not having improvement. 95% CI on proportion of patients having improvement will be implemented by using Clopper Pearson method.

The derived binary variable described in the previous step will then be used in a logistic model as dependent variable; treatment (3 levels: rhNGF \blacksquare mcg/mL, rhNGF \blacksquare mcg/mL, and vehicle) and baseline Schirmer-I scores in the Study Eye as covariates.

Based on this modeling, the estimated proportions and corresponding two-sided 95% CI will be provided for each treatment arm; the estimated mean proportion differences, two-sided 95% CI, and corresponding one-sided p-value will be provided for each IMP group versus vehicle at Week 4.

8.2.1.2. Mean change from baseline in Schirmer-I score without anesthesia in the Study Eye at Week 4

The MI procedure described in [Section 8.2.1.1](#) will be applied to impute missing Schirmer-I scores at Week 4. Change from baseline at Week 4 will be fitted in the ANCOVA model with change from baseline at Week 4 as dependent variable, treatment (3 levels: rhNGF \blacksquare mcg/mL, rhNGF \blacksquare mcg/mL, and vehicle) and baseline Schirmer-I scores in the Study Eye as covariates.

Based on this modeling, a point estimate (the adjusted estimated treatment effect), associate SE, two-sided 95% CI, and corresponding one-sided p-value will be provided for each treatment group; a point estimate (the adjusted estimated treatment difference), associate SE, two-sided 95% CI, and corresponding one-sided p-value will be provided for each least squares (LS) mean treatment difference versus placebo at Week 4.

8.2.1.3. Mean change from baseline in total corneal fluorescein staining (NEI scale) in the Study Eye as assessed by the investigator at week 4

Corneal fluorescein staining has 5 zones and each zone has a score range of 0-3. The total score is determined by simply adding up the scores of the 5 individual zones. The range of total corneal fluorescein staining in NEI scale is 0-15. If any of the 5 individual zones has a missing score, the total score would be missing.

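### For the week-4 Study Eye key secondary endpoints, the prohibited-medication event has no eye condition, so use in the fellow eye alone sets an observed Study Eye value to missing

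*SAP*

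**What the plan says.** Table 5 in SAP 13.4 classifies a medication as prohibited on three conditions: ATC2 class S01, one of four listed routes, and an end date after consent. Note 1 states: "All three conditions need to be satisfied to classify the medication as PROHIBITED". Note 2 sets a date-imputation rule for partial start dates and gives its purpose: "To identify the impacted measurements taken within one week after taking these prohibited medications". That link between product and measurement is by time only.

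In SAP 3.3.2 the event for key secondary objectives 1 and 2 is "Use of a prohibited medication, in the week before any assessment of Schirmer-I score", and the consequence is that "any data collected in the week after the occurrence of the ICE will be discarded". For objective 3 the variable name is redacted in the SAP, but Protocol 3.2.2 shows the same rule: "Use of a prohibited medication listed in § 6.6.1 in the week before any assessment of corneal fluorescein staining". No eye is named in any of these definitions.

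The gap is then filled. SAP 8.2.1.1 says: "Missing data will be imputed by using a multiple imputation with copy-reference approach". It points to SAP 8.1.1, which specifies fully conditional imputation "where only the subset of observations that come from the Vehicle group are used to derive the imputation model". SAP 8.2.1.2 and 8.2.1.3 reuse the procedure.

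Laterality is used elsewhere. SAP 7.1.3 says: "Ophthalmic prohibited medications will be summarized for the study eye and fellow eye separately". SAP 7.1.2 does the same for concomitant ophthalmic medications, SAP 7.3.1 counts extra IMP administrations only when given in the study eye, and SAP section 4 separates eye-level assessments from patient-level ones, with SANDE as an example of the latter.

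**The concern.** All three key secondary endpoints are read in one eye. A drop put only in the other eye triggers the event in the same way as a drop in the Study Eye, so a reading from an eye that did not receive the product is set aside. For an rhNGF patient the replacement is a prediction for a vehicle patient with the same baseline, which removes that patient's drug effect from the comparison.

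The endpoints exposed are the only sign endpoints under alpha control. The plan itself puts their power at about 67% in its worst-case Hochberg step, so there is little to spare. Unilateral use is plausible: Protocol 6.6.3 lets the physician give appropriate treatment without a predefined rescue product, and Table 5 captures any S01 product by the listed routes. The SAP gives no reason for ignoring laterality here while using it elsewhere.

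**Working it through.** **1. Following the rule for one patient.** Take an rhNGF patient who uses an S01 topical product in the fellow eye alone, five days before Visit 4.

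| Step | Source | Eye considered? | Result |
|---|---|---|---|
| Is the product prohibited? | SAP 13.4, Table 5 | No | Yes |
| Is the Visit 4 reading within a week of use? | SAP 13.4, Note 2 | No | Yes |
| Does the event apply to Schirmer-I and staining? | SAP 3.3.2; Protocol 3.2.2 | No | Study Eye values set to missing |
| How are they replaced? | SAP 8.1.1, 8.2.1.1–8.2.1.3 | – | Imputed from the vehicle model |

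The masked medication review in SAP 7.1.3 covers presence, frequency and dosage, to grade the deviation. It does not exempt fellow-eye use from the event.

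**2. Reach.** The rule applies to the three week-4 key secondary analyses, and to the baseline value if use falls in the week before Visit 2. SAP 8.2.2 keeps observed data for the other secondary endpoints whatever the intercurrent events, except SANDE at week 4, which follows the primary rule and is a patient-level score.

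**3. The plan's own figures.** Inputs from Protocol 10.1: mean changes −28.2 (SD 26.36) and −17.4 (SD 20.29), one-sided alpha 0.0125 per comparison, 80% power, 5% not evaluable.

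- Difference: 28.2 − 17.4 = 10.8.
- SD: √[(26.36² + 20.29²)/2] = √(1106.53/2) = 23.52.
- The normal approximation gives 91 per group. The unequal-variance t-test gives 92, with power 80.2%. The plan's 92 is reproduced.
- 276/0.95 = 290.5, so 291 enrolled. Reproduced.
- Smallest Hochberg level: 0.0125/3 = 0.00417. Power at 92 per group: 67.2%. The 67% in Protocol 10.6.4 and SAP 8.2.1 is reproduced, using the SANDE effect.

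**4. Dilution.** Let f be the share of active-arm week-4 values replaced because of fellow-eye-only use. Vehicle values replaced from the vehicle model keep about the same mean. If affected rhNGF patients would have had the average effect, the expected difference is about

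(1 − f) × true difference.

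The documents give neither f nor a planning effect for Schirmer-I or staining. The table therefore assumes f and borrows the SANDE standardised effect (10.8/23.52 = 0.459), with 92 per group and one-sided alpha 0.00417.

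| f (assumed) | Patients per active arm (92 × f) | Standardised effect | Power |
|---|---|---|---|
| 0 | 0 | 0.459 | 67.2% |
| 1% | 0.9 | 0.455 | 66.0% |
| 2% | 1.8 | 0.450 | 64.9% |
| 3% | 2.8 | 0.445 | 63.7% |
| 5% | 4.6 | 0.436 | 61.4% |
| 10% | 9.2 | 0.413 | 55.4% |

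Only the shift in the mean is counted; any extra variance from imputation is not.

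**The case against.** The best defence is that the rule follows the stated estimand. The key secondary estimands ask what would have happened had prohibited products been unavailable to the patient in the week before evaluation. Protocol 6.6.1 prohibits them per patient, study product goes into both eyes, and the log of Amendment 1 records the estimands as added at FDA request. On this view an eye-specific trigger is a different estimand. This does not settle the matter. If a fellow-eye drop does not act on the Study Eye, the observed reading already is the value under no prohibited medication, and a vehicle-based imputation estimates it less well. What stands is that the absence of a cross-eye effect is an assumption, which the documents neither establish nor rule out.

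The argument on size also stands. Protocol 5.2 excludes active infection in either eye, other disorders needing topical medication, chronic conjunctivitis and severe blepharitis, and any added ophthalmic treatment is a protocol deviation. The event needs fellow-eye-only use within a week of the visit. An assumed 5% would equal the plan's whole allowance for patients not evaluable for the primary analysis. Key secondary testing takes place only for a concentration that has won on SANDE, and SAP 8.2.1 also presents descriptive statistics on observed data, so the readings remain visible in the report.

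A reader might infer that the Per Protocol exclusion makes this worse. Fellow-eye use does count as intake of a prohibited medication under SAP 5.2, but the only Per Protocol analysis specified is of SANDE (SAP 8.1.2), where an either-eye rule is coherent.

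**Conclusion.** The gap is real and minor. As written, fellow-eye-only use of an S01 product within a week of the assessment removes an observed Study Eye value from the three week-4 key secondary analyses and, in the rhNGF arms, replaces it with a vehicle-based imputation. The result is a dilution toward no difference of about f. Because f is not documented, the power figures show sensitivity and do not forecast a loss; a share toward the low end of the table is more likely than one toward the high end.

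Three stronger readings are not supported. Study Eye data are not lost throughout the trial, because the week-8 Schirmer-I and staining analyses keep observed values. There is no inflation of false positives, because the replacement pulls the active arms toward vehicle. And the definition of a prohibited product in Table 5 is not itself wrong: Protocol 6.6.1 names no eye, and SAP 7.1.3 expects fellow-eye use to be counted as prohibited.

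The conclusion rests on no cross-eye effect and on affected patients having about the average treatment effect.

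**What to change.** Leave the Table 5 definition, the deviation rule and the Per Protocol rule as they are. A fourth condition inside Table 5 would relabel fellow-eye use as not prohibited, against Protocol 6.6.1 and SAP 7.1.3.

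In Note 2 of SAP 13.4 and in the three event definitions of SAP 3.3.2, state that for Study Eye endpoints a measurement is impacted only if the prohibited product was given to the study eye, to both eyes, or by a route that is not eye-specific, such as nasal. Treat missing laterality as study eye. Keep the either-eye rule for SANDE. Optionally, repeat the key secondary analyses under the patient-level rule as a sensitivity analysis. If the sponsor prefers that rule as the main one, the SAP should say so and give the reason.

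The cost is one programming condition, on laterality that the SAP already uses for its tables, plus an edit to the event wording, to be made before unmasking. SAP section 1 makes the SAP govern where it differs from the protocol. The price is the assumption that fellow-eye use leaves the Study Eye unaffected, which the sensitivity analysis would test.
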